9 INVESTIGATIONAL PLAN

9.1 Overall Study Design and Plan

This study is a 24-month treatment, multicenter, double-blind, placebo-controlled, parallel-group study in EAD including MCI due to AD (Albert, et al., 2011) and the early stages of mild AD. In addition, the MCI due to AD population will also be consistent with the research criterion for “Prodromal AD” (Dubois, et al., 2010) in that episodic memory will be impaired on a list learning task (ISLT). An open-label Extension Phase will be available for subjects who complete the full 24 months of treatment in the Core study. The Extension Phase will continue until commercial availability of elenbecestat (E2609), or until a positive risk-benefit assessment in this indication is not demonstrated. Full details of the Extension Phase will be available in a future protocol amendment. A total of 1330 subjects will be randomized, in a double-blind manner, to receive either placebo or elenbecestat (E2609) 50 mg per day (approximately 1:1 randomization ratio) for 24 months. Randomization will be stratified according to region (7 levels), clinical dementia staging with no more than approximately 25% of the randomized subjects diagnosed with the early stages of mild dementia due to AD, and concurrent AD medication use. The 7 levels of region are:

1. North America
2. Western Europe (including Oceania region)
3. Eastern Europe
4. Japan
5. China
6. Other Asian countries
7. South America

The study is designed to have more frequent visits focused on safety assessments during the first 3 months of treatment.

Two longitudinal biomarker substudies will evaluate the effects of study treatment on the underlying pathophysiology of AD using amyloid PET and/or CSF biomarkers. Participation in the substudies is optional and will require specific consent that will not affect enrollment or treatment in the main study.

The maximum estimated duration for each subject on study is approximately 29 months (ie, 2-month Prerandomization Phase, followed by 24 months of treatment and a 3-month Follow-Up Phase).

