9.7 Statistical Methods

All statistical analyses will be performed by the sponsor or designee. Statistical analyses will be performed using SAS software or other validated statistical software as required.

All statistical tests will be based on the 5% (2-sided) level of significance, unless specified.

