9.7.1.6.1 PRIMARY EFFICACY ANALYSIS

The primary analysis will be based on an intent to treat philosophy without regard to adherence to treatment. The primary analysis of the change from baseline in CDR-SB at 24 months will be performed to compare elenbecestat (E2609) 50 mg per day versus placebo using a linear mixed effects model for repeated measures (MMRM) on the FAS. The MMRM model will include baseline CDR-SB as a covariate, with treatment group, visit, randomization stratification variables (ie, region [7 levels], clinical dementia [yes, no], and concurrent AD medication use at randomization (Visit 2) [yes, no]), and treatment group-by-visit interaction as fixed effects. An unstructured covariance matrix will be employed to model the covariance of within subject effect; if MMRM fails to converge then a covariance structure with fewer parameters from the following list will be employed according to the prespecified order in the list until the MMRM converges. The list of covariance structure will include Heterogeneous Toeplitz, Toeplitz, Heterogeneous Compound Symmetry, and Compound Symmetry. This primary analysis will include all observed post baseline data of the change from baseline in CDR-SB without imputation of missing values. The treatment effect for elenbecestat (E2609) versus placebo will be compared at 24 months based on MMRM model. The LS means and difference in LS means between elenbecestat (E2609) treatment group and placebo, and corresponding 95% CI will be presented.

The null hypothesis is that there is no difference in the mean change from baseline in CDR-SB at 24 months between elenbecestat (E2609) 50 mg per day and placebo. The corresponding alternative hypothesis is that there is a difference in the mean change from baseline in CDR-SB at 24 months between elenbecestat (E2609) 50 mg per day and placebo.

The primary analysis will be repeated to minimize the impact of change in concomitant AD medications where efficacy data after initiation of new AD medications and increase of current AD medications will be censored.

The following sensitivity analysis will be conducted to evaluate the impact of missing data: the primary endpoint will be analyzed using ANCOVA after multiple imputation. The ANCOVA model will include baseline CDR-SB as a covariate, with treatment group and randomization stratification variables as factors.

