9.7.2 Determination of Sample Size

The sample size for this study is estimated based on comparison of elenbecestat (E2609) versus placebo with respect to the primary efficacy endpoint, the change from baseline CDR-SB at 24 months. Based on available ADNI data [amyloid positive, MMSE equal or greater than 24, late MCI (global CDR=0.5) populations from ADNI, ADNI 2 and ADNI GO] the mean and the standard deviation of the change from baseline in the CDR-SB at 24 months in the placebo group are assumed to be 1.75 and 2.05, respectively. Therefore, assuming a 25% reduction in the mean change from baseline CDR-SB at 24 months for the elenbecestat (E2609) 50 mg per day dose group compared to placebo with a common standard deviation of 2.05 and an estimated 30% dropout rate in this study, a total sample size of 1330 subjects, 665 subjects in each treatment group, will be required to detect the treatment difference between elenbecestat (E2609) 50 mg per day and placebo using a 2-sample t-test with 90% power at a significance level of 2-sided $\alpha=0.05$.

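### The fallback covariance order for the primary MMRM puts constant-variance structures where they would understate the month-24 standard error if reached: an unlikely branch, cheaply repaired

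*Protocol*

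**What the plan says.** The primary analysis in Section 9.7.1.6.1 is an MMRM of change from baseline in CDR-SB, tested at 24 months. The covariance is unstructured first. On non-convergence, simpler structures are tried in a stated order until one converges: "The list of covariance structure will include Heterogeneous Toeplitz, Toeplitz, Heterogeneous Compound Symmetry, and Compound Symmetry". The same sentence stands in the synopsis and in Section 9.7.1.6.1 of the older protocol version bound in the same file.

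Section 9.7 sets the test level: "All statistical tests will be based on the 5% (2-sided) level of significance, unless specified". Section 9.7.2 gives the mean and SD of the 24-month change "in the placebo group are assumed to be 1.75 and 2.05, respectively", with a "common standard deviation of 2.05 and an estimated 30% dropout rate in this study". No SD is given for any earlier visit. CDR is assessed every 3 months during treatment (Section 9.1.2.1 and Table 4), so there are eight post-baseline treatment visits, the last of which carries the test.

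The protocol does not say whether the standard error is model-based or empirical.

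**The concern.** Toeplitz and Compound Symmetry each impose a single variance on all visits. Change from baseline in a progressive disease normally spreads out over time, because subjects decline at different rates. Section 9.7.1.6.2 analyses the same outcome with a random-coefficient slope model, which implies variance that grows with time. A pooled variance then sits below the month-24 variance, and the model-based standard error is too small at the one visit that is tested.

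The order adds to this. With eight visits the structures have these numbers of parameters: unstructured 8×9/2 = 36, Heterogeneous Toeplitz 8+7 = 15, Toeplitz 8, Heterogeneous Compound Symmetry 8+1 = 9, Compound Symmetry 2. If Heterogeneous Toeplitz fails and Toeplitz converges, the rule stops there. Heterogeneous Compound Symmetry, with one more parameter and visit-specific variances, is never tried.

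At stake is the validity of the primary p-value if a fallback is used. Secondary testing opens only if the primary test is significant, and the other continuous secondary endpoints use the same model (Section 9.7.1.6.2), so an error there would carry over.

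**Working it through.** **Design inputs (Sections 9.1, 9.7 and 9.7.2).** Two-sided 5%; placebo change 1.75; reduction 25%, so the difference is 0.25 × 1.75 = 0.4375; SD 2.05; dropout 30%; 90% power; 1:1 allocation.

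**The plan's own figure.** n per arm = 2(1.960 + 1.282)² × 2.05² / 0.4375² = 461.4, so 462. Inflated: 462/0.7 = 660. The t-test version needs 463, inflated to 662. The protocol says "a total sample size of 1330 subjects, 665 subjects in each treatment group, will be required", which is consistent. About 465 completers per arm (665 × 0.7 = 465.5) give 90.2% power.

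**Closed form for Compound Symmetry, complete data.** The fitted common variance tends to the mean of the visit variances, so

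SE ratio = √(mean visit variance / month-24 variance), and type I error = 2[1 − Φ(1.96 × SE ratio)].

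Example with an assumed month-3 SD of 1.0 rising linearly to 2.05:

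- SDs: 1.00, 1.15, 1.30, 1.45, 1.60, 1.75, 1.90, 2.05.
- The squares sum to 19.55, so the mean is 2.444; the month-24 variance is 4.2025.
- Ratio = √(2.444/4.2025) = 0.763; 1.96 × 0.763 = 1.495; type I error = 13.5%.

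The same formula gives 8.0% at a month-3 SD of 1.6, 6.5% at 1.8 and 5.0% at 2.05 (equal variances). A simulation with 465 per arm and 4000 runs gave 13.1% at a month-3 SD of 1.0, and 4.9% when the month-24 variance itself was used.

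**All four structures with 30% dropout.** Dropout was spread evenly over the visits and unrelated to outcome. Three true covariances were assumed:

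- random slope plus independent visit error;
- the same, with half the error variance shared by all visits through the common baseline;
- SD rising linearly, with correlation 0.95 per three-month step.

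For each, the large-sample likelihood fit of each working structure was found, and the model-based standard error of the month-24 contrast was compared with its true value. Type I error in %, range over the three covariances:

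| Assumed month-3 SD | Toeplitz | Compound Symmetry | Het. Compound Symmetry | Het. Toeplitz |
|---|---|---|---|---|
| 0.9 | 15.3-16.4 | 18.1-19.2 | 5.1-6.6 | 5.0-9.3 |
| 1.2 | 12.3-13.1 | 13.8-14.6 | 5.1-6.1 | 5.0-7.4 |
| 1.6 | 8.4-8.8 | 8.9-9.6 | 5.1-5.5 | 5.0-5.9 |
| 1.8 | 6.8-7.0 | 7.0-7.8 | 5.1-5.3 | 5.0-5.4 |

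Two things follow. The constant-variance structures are the worst, by a margin that depends on how fast the SD rises. Heterogeneous Toeplitz is not safe either: under random slopes with a month-3 SD of 0.9 it gives 8.7-9.3%, because its correlation pattern is wrong.

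With equal variances the pooling effect is gone. Compound Symmetry with dropout could still be near 6% if the correlation decays with time, but that is a correlation problem, not a variance one.

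**Effect on the overall error.** If a constant-variance fallback were used with probability q (assumed), overall type I error = 5% + q × (conditional error − 5%). At q = 1% this is 5 + 0.01 × (8.4 − 5) = 5.03% to 5 + 0.01 × (19.2 − 5) = 5.14%. At q = 5% it is 5.17% to 5.71%.

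**The case against.** The strongest objection is that this branch will probably never be used. Toeplitz needs two failures to converge (unstructured, then Heterogeneous Toeplitz), and Compound Symmetry, which supplies the upper end of the range, needs four. With 1330 subjects and eight visits the unstructured fit should converge. That stands, and it sets the severity. A reader might infer that the trial's type I error is 8-19%; the documents do not support that, because the figure applies only after those failures.

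Second, the size rests on early SDs that the protocol does not give. That also stands. Rising variance is plausible, so the direction is likely, but the range is an assumption.

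Third, the choice of standard error is commonly left to the statistical analysis plan, and an empirical one would repair the existing list. Its absence from the protocol is therefore no finding, and the inflation is conditional on a model-based standard error. The list and its order, however, are fixed in the protocol.

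Fourth, the ANCOVA after multiple imputation in Section 9.7.1.6.1 does not pool early variances and could expose too narrow an MMRM interval. It is a sensitivity analysis and does not replace the primary p-value.

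A reader might also infer that deleting the two constant-variance structures is enough. It is not, given the Heterogeneous Toeplitz results.

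**Conclusion.** The point holds in conditional form. The protocol's order reaches a constant-variance structure before a visit-specific one of nearly the same size, and ends on another constant-variance structure. If one of these is used with a model-based standard error and variance rises over time, the primary test is anticonservative: about 8-16% for Toeplitz and 9-19% for Compound Symmetry at an assumed month-3 SD of 0.9 to 1.6 with 30% dropout, and about 7-8% at 1.8. The oddity of the order needs no assumption about early SDs; the size does. Because the branch is remote, the expected effect on overall type I error is small. This is a minor point and a cheap improvement, worth making because a fallback rule should be valid when triggered, and a repair made after a convergence failure would be data-driven.

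**What to change.** Amend the covariance sentence in Section 9.7.1.6.1 and the matching synopsis text, and carry it into the analysis plan:

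- Require the empirical (sandwich) standard error whenever the covariance is not unstructured. This includes Heterogeneous Toeplitz.
- Place Heterogeneous Compound Symmetry directly after Heterogeneous Toeplitz.
- Delete Toeplitz and Compound Symmetry, or keep them only as last resorts with the sandwich standard error.

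The order still matters with a sandwich standard error. The sandwich corrects the standard error, but if dropout depends on earlier outcomes a wrong covariance can also bias the estimate, so the structures closest to unstructured should come first.

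The cost is one sentence and no operational change. The only downside is a slightly wider interval if a fallback is used.

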9.7.1.6.2 SECONDARY EFFICACY ANALYSES

The secondary analyses will be performed only if the primary analysis is significant. The treatment effect for elenbecestat (E2609) 50 mg/day versus placebo, for each secondary efficacy endpoint, will be tested using a sequential testing procedure at a significance level of 2-sided $\alpha = 0.05$, ie, any test will start only if the test with higher hierarchical order is significant. The final hierarchical order will be specified later in the statistical analysis plan before database lock.

Time to worsening of CDR scores by 24 months will be analyzed on the FAS using Cox regression model for treatment effect adjusting for randomization stratification factors. Time to worsening of a CDR score is defined as time from randomization to worsening of the CDR score (ie, the first worsening in 2 consecutive scheduled visits). For subjects whose CDR scores have not worsened by the end of study, the time to worsening of the CDR score will be censored at the date of last CDR assessment for these subjects.

Time to conversion to dementia for subjects who were not clinically staged as dementia at Baseline based on clinical diagnosis will be analyzed on the FAS using Cox regression model for treatment effect adjusting for randomization stratification factors. Proportion of subjects with dementia diagnosis at 24 months will be estimated using Kaplan—Meier method based on time to conversion to dementia based on clinical diagnosis. Time to conversion to dementia for subjects who were not clinically staged as dementia at Baseline based on clinical diagnosis is defined as time from randomization to conversion to dementia based on clinical diagnosis. For subjects without clinical dementia by the end of study, the time to conversion to dementia based on clinical diagnosis will be censored at the date of last dementia diagnosis.

The rate of change over time (mean slope) based on change from baseline in the CDR-SB will be analyzed using linear mixed effects (LME) models for multivariate normal data derived from a random coefficient model (slope analysis), where the mean slope in each group depends on a continuous assessment time. The LME model will include baseline CDR-SB, randomization stratification variables, assessment time, and treatment group-by-assessment time.

The other continuous secondary efficacy endpoints as defined above will be analyzed using the same MMRM model as the primary efficacy analysis to compare elenbecestat (E2609) 50 mg per day versus placebo on the FAS, using baseline value corresponding to the response variable in the model.

The relationship between clinical changes at 24 months (CDR-SB, ADAS-cog₁₄, MMSE, and FAQ) and changes in each of the biomarkers (amyloid PET, CSF A β (1-x), t-tau, p-tau, vMRI, and fMRI) at 24 months, will be evaluated using an ANCOVA model. (revised per Amendment 03) Changes in clinical scales at 24 months will be the response variables and either continuous or categorical change of biomarkers will be independent variables. The ANCOVA model will also include baseline value for clinical scale as a covariate, randomization stratification variables, treatment group as factors, and other terms as appropriate.

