9.3.1 Inclusion Criteria

Subjects must meet all of the following criteria to be included in this study:

1. MCI due to AD or Mild AD according to the National Institute of Aging – Alzheimer’s Association (NIA-AA) core clinical criteria and must have all of the following at Screening: (revised per Amendment 03)
 - a. MMSE score equal to or greater than 24
 - b. CDR global score of 0.5
 - c. CDR Memory Box score of 0.5 or greater
2. A history of subjective memory decline with gradual onset and slow progression over the last 1 year before Screening; this MUST be corroborated by a study partner
3. Cognitive impairment of at least 1 SD from age-adjusted norms in total recall or delayed recall on the ISLT.

4. Positive biomarker for brain amyloid pathology as indicated by at least 1 of the following:
 - a. PET assessment of amyloid imaging agent uptake into brain. Note: amyloid PET screens will be performed according to local regulatory guidelines and thus may be restricted for those subjects who are not suitable for LP to obtain CSF for testing of eligibility.
 - b. CSF AD assessment (eg, A β (1-42), tau: A β (1-42) ratio) (revised per Amendment 03)
NOTE: Subjects may undergo both the amyloid PET and CSF assessments, but need a positive amyloid result in only 1 of the 2 procedures to confirm eligibility. Subjects who consent to amyloid PET or CSF for eligibility purposes are not required to participate in the amyloid PET or CSF longitudinal substudies. Use of a historical amyloid positive PET (conducted within 12 months before the planned date of randomization) is acceptable for determination of eligibility but will not suffice for the baseline assessment if the subject wishes to consent to the amyloid PET longitudinal substudy. (revised per Amendment 03) The historical imaging data must be made available to the sponsor.
5. Male or female subjects between 50 and 85 years of age, inclusive at the time of consent
6. If receiving an AChEI or memantine or both for AD, must be on a stable dose for at least 12 weeks prior to Randomization. Treatment-naïve subjects with AD can be entered into the study.

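### Both Cox secondary analyses omit baseline CDR-SB, which the neighbouring models use; they are valid but may give up power, most plausibly for time to dementia

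*Protocol*

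**What the plan says.** Section 9.7.1.6.2 fixes the covariates of two time-to-event analyses. The CDR-worsening endpoint "by 24 months will be analyzed on the FAS using Cox regression model for treatment effect adjusting for randomization stratification factors". The time to conversion to dementia, for subjects not staged as having dementia at baseline, is "based on clinical diagnosis will be analyzed on the FAS using Cox regression model for treatment effect adjusting for randomization stratification factors". The factors are listed in section 9.7.1.6.1: "region [7 levels], clinical dementia [yes, no], and concurrent AD medication use at randomization (Visit 2) [yes, no". None of them is a baseline score.

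The neighbouring models do use one. For the primary analysis, "The MMRM model will include baseline CDR-SB as a covariate, with treatment group, visit, randomization stratification variables" and further terms enter. For the slope analysis, "The LME model will include baseline CDR-SB, randomization stratification variables, assessment time, and treatment group-by-assessment time". The remaining continuous secondary endpoints use the MMRM with their own baseline value.

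All secondary efficacy endpoints share one sequential procedure at two-sided 0.05, in which a test is made only if the one before it succeeded. Section 9.7.1.6.2 leaves the order to the SAP, to be set before database lock.

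**The concern.** Baseline CDR-SB is a natural prognostic variable for both events. Entry requires, at Screening, a "CDR global score of 0.5" (section 9.3.1). Section 9.7.1.1.2 gives, as its example of worsening, a rise of at least half a point in the global score at two consecutive visits. Section 9.2.1 describes the global score and the sum of boxes as two summaries of the same six domain ratings. Among subjects who share a global score of 0.5, the sum of boxes therefore says something about how near each one is to the next step.

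For CDR worsening, the clinical-dementia factor picks up part of that severity. For time to dementia it cannot, because it takes a single value in the population analysed.

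Leaving a prognostic covariate out of a Cox model moves the treatment hazard ratio towards 1 and lowers power. In a fixed sequence, a missed test also closes every test placed after it.

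**Working it through.** **The plan's own figure.** Section 9.7.2 assumes a placebo change of 1.75, SD 2.05, a 25% reduction, 90% power, two-sided 0.05 and 30% dropout.

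- Difference: 0.25 × 1.75 = 0.4375.
- n per arm = 2(z₀.₉₇₅ + z₀.₉₀)²σ²/δ² = 2 × 10.507 × 4.2025 / 0.1914 = 461.4, so 462.
- Dropout: 462 / 0.70 = 660 per arm, 1320 in total. The exact t calculation gives 463, then 662 per arm, 1324 in total.
- Power with 665 × 0.70 per arm: 90.2%.

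The stated 1330 is reproduced. It concerns the primary endpoint only; the protocol states no event rate, hazard ratio or power for either Cox endpoint.

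**Populations.** CDR worsening: 1330. Time to dementia: if the cap of about 25% with mild dementia is reached, 0.75 × 1330 = 997.5, taken as 998.

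**Assumptions not in the protocol.** Conditional hazard ratio 0.75; placebo 24-month event rate 30% or 50%; prognostic hazard ratio 1.25, 1.5 or 2.0 per SD of baseline CDR-SB; exponential event times; 30% dropout spread exponentially over 24 months; dementia stratum 1 SD higher at baseline; half of subjects on AD medication. Region, the three-monthly visit grid and the two-visit confirmation rule were not simulated.

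**Comparison.** There were 1000 simulated trials per scenario. The reference model holds treatment, AD medication and, for CDR worsening, clinical dementia. The alternative adds baseline CDR-SB.

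| Endpoint | Placebo event rate | HR per SD | Mean events | Power without | Power with | Gain (points) | Estimated HR without / with |
|---|---|---|---|---|---|---|---|
| CDR worsening | 30% | 1.25 | 302 | 67.8% | 68.3% | 0.5 | 0.750 / 0.749 |
| CDR worsening | 30% | 1.5 | 303 | 70.4% | 70.7% | 0.3 | 0.751 / 0.747 |
| CDR worsening | 30% | 2.0 | 306 | 62.1% | 68.5% | 6.4 | 0.766 / 0.751 |
| CDR worsening | 50% | 1.25 | 518 | 91.1% | 91.1% | 0.0 | 0.749 / 0.746 |
| CDR worsening | 50% | 1.5 | 520 | 90.0% | 91.9% | 1.9 | 0.754 / 0.746 |
| CDR worsening | 50% | 2.0 | 528 | 84.5% | 90.6% | 6.1 | 0.771 / 0.748 |
| Dementia | 30% | 1.25 | 226 | 55.7% | 56.2% | 0.5 | 0.754 / 0.753 |
| Dementia | 30% | 1.5 | 228 | 56.5% | 58.0% | 1.5 | 0.754 / 0.749 |
| Dementia | 30% | 2.0 | 230 | 51.5% | 56.1% | 4.6 | 0.764 / 0.750 |
| Dementia | 50% | 1.25 | 388 | 79.0% | 79.5% | 0.5 | 0.756 / 0.753 |
| Dementia | 50% | 1.5 | 390 | 78.4% | 80.6% | 2.2 | 0.759 / 0.749 |
| Dementia | 50% | 2.0 | 396 | 74.0% | 82.6% | 8.6 | 0.770 / 0.749 |

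The Monte Carlo error of each power is about 1 to 1.6 points; the paired differences are more precise. No scenario showed a loss from adjusting.

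**Cross-check.** Schoenfeld's formula, 4(z₁₋α/₂ + z₁₋β)²/(ln HR)², asks for 380 events for 80% power and 508 for 90% at a hazard ratio of 0.75. Roughly 300 events for CDR worsening or 230 for dementia fall short of 380, in line with the simulated power at the 30% event rate.

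**The case against.** A Cox model adjusted for the randomization factors is a sound prespecified analysis, and nothing in the protocol contradicts it: own-baseline adjustment is promised only for the continuous endpoints. That stands. The point is one of efficiency, not of validity.

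The gain is uncertain. The protocol does not say how prognostic baseline CDR-SB is, and at 1.25 to 1.5 per SD the benefit is hardly visible. That also stands.

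Three stronger readings are tempting but not supported:

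- **The two endpoints come early in the testing sequence.** A reader might infer this because they head the list in section 9.7.1.1.2. That list is not declared to be the testing order, and section 9.7.1.6.2 defers the order to the SAP. If the SAP puts them last, a miss blocks nothing.
- **The gain for CDR worsening is 6 to 11 points.** Such figures arise if the event is modelled as CDR-SB crossing a cut-off such as 4.5, with an assumed baseline SD of 1.0 to 1.2. Neither value is in the protocol. The global score comes from an algorithm on the domain ratings, and conversion is a staging decision with central verification, so a crossing rule builds in strong prognosis. With a baseline SD of 0.7 or a cut-off of 5.5, the same approach gives 1 to 2 points.
- **The dementia model has no severity adjustment whatever.** AD medication use may act as a partial proxy.

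**Conclusion.** The point holds as a cheap improvement. Both Cox models omit a baseline measure that the trial already collects and that the neighbouring CDR-SB models use, and the protocol gives no reason for the difference. The likely cost is about 0 to 2 points of power if baseline CDR-SB is weakly or moderately prognostic, and about 5 to 9 points if it is strongly prognostic (hazard ratio 2.0 per SD), where the unadjusted hazard ratio drifts from 0.75 to about 0.76 to 0.77. These sizes rest on the assumed hazard ratio, event rates and prognostic strengths listed above.

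The case is strongest for time to dementia, because there the clinical-dementia factor contributes nothing; that part follows from the text without simulation. How far a miss would carry depends on an order that the protocol has not set.

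**What to change.** In section 9.7.1.6.2, the matching synopsis text and the SAP, have both Cox models adjust for the randomization stratification factors and for baseline CDR-SB as a continuous covariate. Make the change before unblinding, and keep the currently specified models as supportive analyses. The clinical-dementia factor may be removed from the time-to-dementia model for tidiness; being constant there, its removal changes no estimate.

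The cost is a sentence of text and no new data. The small downside is that the treatment hazard ratio becomes conditional on baseline CDR-SB, which the report should state.
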